### 4.1 Safety and Tolerability

The safety and tolerability of ipilimumab and nivolumab in combination with RT will be determined. Safety will be evaluated by the internal data safety monitoring panel on an ongoing basis, based on data review and regular conference calls with the investigators.

#### 4.1.1 Endpoints & Assessment Methods

Clinical laboratory tests, vital sign measurements, physical examinations, and subject interviews will be performed to detect new abnormalities and deteriorations of any pre-existing conditions. The investigator will evaluate any laboratory abnormalities for clinical significance, and clinically significant abnormalities will be recorded as AEs. All treatment-emergent, clinically significant abnormalities and deteriorations from the time of informed consent to the End of Study Visit should be recorded in the eCRFs as AEs and graded according to the National Cancer Institute (NCI) Common Terminology Criteria for Adverse Events (CTCAE), Version 4.03.

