#### Cohort A:

Subjects in Cohort A will initially receive a conventional total RT palliative dose of 30 Gy delivered over 2 weeks in 10 fractions of 3 Gy each. Once 9 subjects have been accrued to Cohort A and completed the concurrent ipilimumab and nivolumab therapy, if  $\leq 7$  subjects have Grade 3 or 4 drug- or radiation-related AEs, as per Section 3.1.6, the safety of Cohort A will be deemed acceptable and additional subjects will be accrued to Cohort B.

Note: Grade 3 or 4 amylase or lipase abnormalities that are not associated with clinical symptoms will not be included in the Cohort A safety assessment described above.

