### 3.1.6 Sample Size and Statistical Considerations

This study is intended to generate descriptive safety data. Nine subjects are anticipated for each cohort to enable a variety of disease presentations and RT targets.

Prior experience with nivolumab and ipilimumab administered in combination has been associated with a treatment-related grade 3/4 toxicity rate of 53%. A rating of Grade 3/4 drug- or radiation-related toxicity is considered to be acceptable in Cohort A if  $\leq 7$  of 9 subjects (78%) are affected (see exception in Section 3.1, i.e., asymptomatic amylase and lipase abnormalities are not included). This number was selected to avoid premature closure of exploration of this approach.

As this is the first prospective study of RT plus ipilimumab and nivolumab, no historical controls are available to anticipate the rate of toxicity of this triple combination regimen.

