### 3.1.9 Dose-limiting Toxicity

The DLT and MTD will not be defined or determined. A safety review will be conducted when 9 subjects have been accrued to Cohort A and completed the concurrent ipilimumab and nivolumab therapy. If  $\leq 7$  subjects have Grade 3 or 4 drug- or radiation-related AEs, the safety of Cohort A will be deemed acceptable and additional subjects will be accrued to Cohort B. The Cohort A assessment period for this evaluation will include the first 2 cycles of treatment, up to and including the pre-dose safety assessments scheduled for Cycle 3 (see Section 4.1.2).

Note: Grade 3 or 4 amylase or lipase abnormalities that are not associated with clinical symptoms will not be included in the Cohort A safety assessment described above.

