## 7 Administrative, Legal & Ethical Requirements

### 7.1 Documentation and Reporting of Adverse Events

#### 7.1.1 General AE/SAE Definitions per ICH Guidelines

An **Adverse Event (AE)** is any untoward medical occurrence in a patient or clinical investigation subject administered a pharmaceutical product and that does not necessarily have a causal relationship with the treatment. An AE can therefore be any unfavorable and unintended sign (including an abnormal laboratory finding), symptom, or disease temporally associated with the use of a medicinal (investigational) product, whether or not related to the medicinal (investigational) product.

N.B.: The definition above, provided for in the GCP-ICH Guideline E6, is being extended for the purpose of LICR studies to include any events, intercurrent diseases and accidents observed while the subject is on study, i.e., during the actual treatment period, as well as during drug-free, pre- and post-treatment periods.,

A **Serious Adverse Event (SAE)** is any untoward medical occurrence that:

1. Results in death,
2. Is life-threateningA,
3. Requires inpatient hospitalization or prolongation of existing hospitalization,
4. Results in persistent or significant disability or incapacity,
5. Is a congenital anomaly / birth defect or
6. Is another medically important conditionB.

A The term “life-threatening” in the definition of “serious” refers to an event in which the patient/subject is at risk of death at the time of the event; it does not refer to an event, which hypothetically might have caused death if it were more severe.

B Medically important conditions that may not result in death, be immediately life-threatening or require hospitalization may be considered as SAE when, based upon appropriate medical judgment, they may jeopardize the patient/subject or may require intervention to prevent one of the outcomes listed in the definition above. Examples of such events are intensive treatment in an emergency room or at home for allergic bronchospasm; blood dyscrasias or convulsions that do not result in hospitalization; or development of drug dependency or drug abuse.

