### 7.1.3 Severity of an Adverse Event

The severity of all serious and non-serious AEs should be assessed according to the NCI CTCAE Scale (Version 4.03).

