### Criteria for Dose Delay

Because of the potential for clinically meaningful immuno-oncology-related AEs requiring early recognition and prompt intervention, management algorithms have been developed for the following suspected AEs: diarrhea/colitis; elevated creatinine; pneumonitis; elevated liver function tests (LFTs); elevated TSH; rash; and neurological AEs (see Section 8.3.1).

Dose delay criteria apply to all drug-related AEs (regardless of whether or not an event is attributed to nivolumab, ipilimumab, or both). All study drugs must be delayed until criteria for resumption of treatment are met.

Nivolumab and ipilimumab administration should be delayed for the following:

- Any Grade  $\geq 2$  non-skin, drug-related AE, with the following exceptions:
  - Grade 2 drug-related fatigue or laboratory abnormalities do not require a treatment delay.
- Any Grade 3 skin, drug-related AE.
- Any Grade 3 drug-related laboratory abnormality, with the following exceptions for asymptomatic amylase or lipase, AST, ALT, or total bilirubin:
  - Grade 3 amylase or lipase abnormalities that are not associated with symptoms or clinical manifestations of pancreatitis do not require a dose delay. It is recommended to consult with the Sponsor for Grade 3 amylase or lipase abnormalities.
  - If a subject has a baseline AST, ALT, or total bilirubin that is within normal limits, delay dosing for drug-related Grade  $\geq 2$  toxicity.
  - If a subject has baseline AST, ALT, or total bilirubin within the Grade 1 toxicity range, delay dosing for drug-related Grade  $\geq 3$  toxicity.
- Any AE, laboratory abnormality, or intercurrent illness that, in the judgment of the investigator, warrants delaying the dose of study medication.

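### Section 4.1.1 ties AE recording of laboratory abnormalities to an undefined judgment of clinical significance, so related Grade 3/4 laboratory values can be left out of the graded AE rate and the Cohort A count

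*Combined protocol and SAP*

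**What the plan says.** Section 4.1.1 sets the recording rule for the primary safety endpoint: "The investigator will evaluate any laboratory abnormalities for clinical significance, and clinically significant abnormalities will be recorded as AEs". The next sentence repeats the condition: "All treatment-emergent, clinically significant abnormalities and deteriorations from the time of informed consent to the End of Study Visit should be recorded in the eCRFs". It is these entries that become AEs and receive a CTCAE Version 4.03 grade. Neither sentence defines clinical significance, and neither says that a value of a given grade is significant by default.

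The Cohort A rule counts subjects with AEs. Section 3.1.9 applies it when no more than seven "subjects have Grade 3 or 4 drug- or radiation-related AEs, the safety of Cohort A will be deemed acceptable". Sections 3.1 and 3.1.9 carry one exclusion from the count: "Grade 3 or 4 amylase or lipase abnormalities that are not associated with clinical symptoms will not be included".

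Two other sections deal with laboratory findings and set no significance condition. Section 7.1.1 states: "An AE can therefore be any unfavorable and unintended sign (including an abnormal laboratory finding), symptom, or disease". Section 8.3 lists this among the reasons for delaying a dose: "Any Grade 3 drug-related laboratory abnormality, with the following exceptions for asymptomatic amylase or lipase, AST, ALT, or total bilirubin".

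Section 4.1.2 plans summaries of laboratory data next to the AE summaries, but does not say that the laboratory values will be CTCAE-graded.

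**The concern.** In 4.1.1 the significance judgment comes before grade. A related Grade 3 creatinine value that one investigator regards as not clinically significant need not be entered as an AE under 4.1.1, while a colleague at another site who works from 7.1.1 may enter it. Both would be following the protocol.

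The exemption for asymptomatic amylase and lipase makes the mismatch visible. It has a purpose only if other asymptomatic Grade 3/4 laboratory values are meant to count, yet 4.1.1 does not secure that they do.

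Two results depend on this. The first is the descriptive Grade 3/4 AE rate, which is the main product of the study. The second is the decision to open Cohort B. Compared with counting every related Grade 3/4 value, the judgment can only lower both. It is made without blinding (3.1.3). The reviewing panel is internal and includes the Principal Investigators (3.1.14).

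Evaluability is touched as well. Under 3.1.11 a Cohort A subject with a related Grade 3/4 AE is evaluable on that ground alone. If the only such event is not recorded, the subject must meet the per-protocol criteria or be replaced.

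**Working it through.** **Inputs.** From the documents: 9 subjects in Cohort A and acceptance at 7 or fewer (3.1.6, 3.1.9); a reference Grade 3/4 rate of 53% for the two drugs without radiotherapy (3.1.6). Not in the documents, so assumed: the true rate p for the triple combination (70%, 80% and 90% shown beside 53%), and the share f of affected subjects whose only countable Grade 3/4 event is a laboratory value judged not clinically significant (10% and 20% shown). Here p is the rate after the amylase/lipase exemption.

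**The plan's own figure.** 7/9 = 77.8%, which rounds to the stated 78%. The plan gives no alpha, power or sample-size formula, so there is nothing else to reproduce.

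**Chance of failing the rule.** With X the number of counted subjects and subjects independent,

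P(fail) = P(X ≥ 8) = 9 q⁸(1 − q) + q⁹, where q = p(1 − f).

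At p = 0.80:
- f = 0, q = 0.80: 9 × 0.1678 × 0.20 + 0.1342 = 0.436
- f = 0.10, q = 0.72: 9 × 0.0722 × 0.28 + 0.0520 = 0.234
- f = 0.20, q = 0.64: 9 × 0.0281 × 0.36 + 0.0180 = 0.109

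| True rate p | f = 0 | f = 10% | f = 20% |
|---|---|---|---|
| 53% (cited) | 3.0% | 1.4% | 0.6% |
| 70% (assumed) | 19.6% | 9.8% | 4.4% |
| 80% (assumed) | 43.6% | 23.4% | 10.9% |
| 90% (assumed) | 77.5% | 46.7% | 23.4% |

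**At the boundary.** If exactly 8 of 9 are truly affected, losing any one of them produces a pass. The chance of that is 1 − (1 − f)⁸: 57% at f = 10% and 83% at f = 20%.

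**Effect on the reported rate.** The expected recorded rate is p(1 − f). At 53% it becomes 47.7% or 42.4%, which is 4.3 or 3.8 of 9 subjects against 4.8.

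**The case against.** The best case for the plan is that its sections, read together, already require such values to be recorded. Section 4.1.1 does not forbid entering other laboratory values. Section 7.1.1 includes abnormal laboratory findings, and 7.1.5 requires all AEs to be documented. A reader might infer from 4.1.1 that a Grade 3 value judged not significant can never be an AE; with 7.1.1 and 7.1.5 in the same protocol, the documents do not support that. What they support is that the value can be left out.

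Section 8.3 also helps the plan. Some of its rules treat graded laboratory abnormalities as a kind of AE, although the Grade 4 discontinuation rule names them separately. A drug-related Grade 3 ALT rise delays dosing from either baseline that 8.3 describes, and 7.1.5 makes study-drug intervention part of the AE record. A value that holds treatment would usually be called significant. The amylase/lipase note suggests that the sponsor itself expects such values to count, and 3.1.6 words the rule as toxicity, not as AEs.

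There are other protections. The panel includes the sponsor's medical monitor and the drug provider's safety staff, reviews data on an ongoing basis, and may act on any related safety finding. Scheduled laboratory results are held in the eCRF and summarized.

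These points lower the likely loss. None of them requires a Grade 3/4 value to be recorded as an AE, and laboratory summaries without grades do not feed a rule that counts Grade 3/4 AEs.

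**Conclusion.** The inconsistency is real, and related Grade 3/4 laboratory values can fall out of the CTCAE-graded AE rate and the Cohort A count. The documents do not show that this will happen, or that the count will be too low. They give no figure for the share of subjects affected.

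At the only rate the plan cites, 53%, the effect on the decision is small: the chance of failing goes from 3.0% to 1.4% or 0.6%. It becomes material only if the true rate is high, for example from 44% to 23% or 11% at 80%. That result rests on two assumptions: the high rate, for which 3.1.6 says there is no historical control, and the 10% or 20% loss. To be lost, a subject must have no other related Grade 3/4 event in the two-cycle assessment period, and the sole event must be a non-exempt laboratory value that was dismissed.

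This is a cheap and worthwhile improvement to how the primary endpoint is ascertained. It does not invalidate the study.

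**What to change.** Align 4.1.1 with 7.1.1 by adding a sentence to this effect: every post-baseline laboratory value of CTCAE Grade 3 or higher that is worse than the baseline grade is recorded as an AE with a relatedness assessment, whatever its clinical significance; the clinical-significance judgment applies to Grade 1-2 values only.

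In 4.1.2, derive CTCAE grades from the eCRF laboratory data and tabulate the worst post-baseline grade per subject. Give this table to the panel at the Cohort A review. Keep the asymptomatic amylase/lipase exemption as the only exclusion from the count. The dosing rules in 8.3 are not touched.

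**Cost.** One sentence, one programmed check and one table. The chemistry and hematology values are already scheduled at every treatment visit. The flowchart note limits eCRF capture to the charted assessments, so values from unscheduled tests may be missing from the derived table and would depend on the new sentence.

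**Downside.** There will be more AE entries, including some transient values, and a slightly less favorable Grade 3/4 rate. Attribution still rests with the same investigator (7.1.4), so the change narrows the problem without removing it.

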#### 4.1.2 Subject Evaluation & Statistics

The Intent-To-Treat (ITT) Population for safety and tolerability is defined as all subjects who receive at least one dose of study drug or RT. The Per-Protocol (PP) Population for safety and tolerability is defined as all subjects who received at least 75% of the scheduled doses of study drugs and RT over the first 2 cycles, as well as, respective safety assessments (up to and including the pre-dose assessments scheduled for Cycle 3) without major protocol violations over the entire Cohort A concurrent ipilimumab and nivolumab assessment period (as defined in Section 3.1.9).

For both cohorts, the overall analysis of safety and tolerability will be based on the ITT Population.

Appropriate summaries of AEs, laboratory data, and vital sign data will be presented. AEs will be listed individually per subject according to the NCI CTCAE, Version 4.03, and the number of subjects experiencing each AE will be summarized using descriptive statistics.

CONFIDENTIAL

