### **3.1.12 Optional Study Treatment Extension**

Treatment extension with nivolumab monotherapy beyond 18 weeks is permitted and will be managed at the Investigator's discretion in accordance with standard practice. Subjects who require additional treatment will continue to be followed for efficacy assessments and On Study Follow-up (see Section 3.1.16 and Section 3.2). Details of extended nivolumab monotherapy administration should be captured on the Drug Administration electronic case report form (eCRF).

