### **3.1.16 On Study and Post-Study Follow-up**

All subjects, whether they complete the study as planned, discontinue treatment, or prematurely withdraw from the study as per Section 3.1.10, will be followed as per institutional guidelines in accordance with the usual standard of care principles.

On Study Follow-up will be conducted for 100 days after the last study drug administration according to the flowchart in Section 3.2. Refer to Section 7.1.5 for information on recording AEs during the On Study Follow-up.

In addition to the On Study Follow-up, there will be a Post Study Follow-up, during which clinical outcomes data (dates of progression/relapse and survival) will be collected at least every 12 ( $\pm$  1) weeks for 3 years after completion of 100-day On Study Follow-up. For subjects who do not continue Post Study Follow-up at one of the study sites after the end of study, the Principal Investigators or the clinical team, under the supervision of the Principal Investigator, will obtain the data through review of outside records or communication with the subject or his/her physician.

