e For females of child-bearing potential (as defined in Section 5.2), pregnancy tests required every 6 weeks and repeated at 30 (±4) days and 70 (±4) days after discontinuation of treatment. Serum pregnancy test is done at screening, final assessment, and during On Study Follow-up; urine pregnancy test is done at all other visits, including during continued nivolumab treatment (Note: For females of child-bearing potential who are continuing on nivolumab after Week 18 at 480 mg every 4 weeks, urine pregnancy tests may be done every 8 weeks). Urine pregnancy test is done and results confirmed pre treatment on Day 1 of study.

f All subjects will receive concurrent nivolumab (1 mg/kg) followed by ipilimumab (3 mg/kg) on the same day every 3 weeks for 4 doses, then followed by nivolumab monotherapy (240 mg every 2 weeks ±3 days) See footnote d for ongoing nivolumab monotherapy after Week 18. Radiotherapy will be initiated after the first dose and before the second dose of immunotherapy.

g Per Amendment 5: After Week 18, LDH testing and TSH (with reflexive free T3/T4) testing during ongoing nivolumab treatment will be done as clinically indicated; other testing will continue per flowchart.

CONFIDENTIAL

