### 7.1.5 General Reporting Requirements

Documentation of serious and non-serious AEs includes: dates of onset and resolution, severity, seriousness, study drug intervention, treatment and outcome, as well as the causal relationship between the event and the study drug in accordance with Section 7.1.4.

All serious and non-serious AEs occurring between the date of signing the informed consent and the off-study date must be documented in the source records and on the respective section of the CRF, regardless of the assumption of a causal relationship.

During the On Study Follow-up period, all AEs (not only those deemed to be treatment-related) will continue to be collected for 100 days after the last dose of study drug administration.

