**For those subjects who are continuing on nivolumab after Week 18 at 480 mg every 4 weeks  $\pm$  3 days, Study Visits will continue every 4 weeks  $\pm$  3 days during treatment, followed by the Final Assessment Visit, On Study Follow-up, and Post Study Follow-up after the last nivolumab treatment.**

Subjects continuing nivolumab monotherapy, **and** subjects who complete study treatment as responders, **and subjects who have not progressed (either in irradiated or non-irradiated tumor burden)** will have an additional scan (disease assessments by RECIST 1.1/irRECIST) at Week 24 and subsequent scans Q12W ( $\pm$  7 days) until progression or start of alternate anti-cancer therapy.

- Footnote e: the following note was added: “For females of child-bearing potential who are continuing on nivolumab after Week 18 at 480 mg every 4 weeks, urine pregnancy tests may be done every 8 weeks.”
- Footnote f was updated to provide clarification (changes in bold): “All subjects will receive concurrent nivolumab (1 mg/kg) followed by ipilimumab (3 mg/kg) on the same

CONFIDENTIAL

day every 3 weeks for 4 doses, then followed by nivolumab monotherapy (240 mg every 2 weeks  $\pm$ 3 days). **See footnote d for ongoing nivolumab monotherapy after Week 18.** Radiotherapy will be initiated after the first dose and before the second dose of immunotherapy.

- Footnote g was added to reflect current requirements for LDH and thyroid testing; the change was added only for ongoing treatment period after Week 18 to allow for the core study to have consistent collection of data.
- Section 5.1, Exclusion Criterion # 14 was clarified (changes in bold): “Any condition that, in the clinical judgment of the treating physician, is likely to **interfere with the interpretability of the data** or prevent the subject from complying with any aspect of the protocol or that may put the subject at unacceptable risk.”
- Section 6.1.2 (Nivolumab Preparation and Administration). “Additional information” was added per instructions provided by BMS (added last 2 paragraphs).
- Administrative changes: General spelling, grammar, capitalization, and formatting changes, as needed.
- Section 8.7 (Abbreviations) was updated.

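### Section 4.1.2 counts subjects with each adverse event over no common window, so the primary safety counts depend partly on how long nivolumab was continued

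*Combined protocol and SAP*

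**What the plan says.** Safety is the primary objective (Section 4). Section 4.1.2 bases the overall safety analysis of both cohorts on "all subjects who receive at least one dose of study drug or RT". AEs are listed by subject, and "the number of subjects experiencing each AE will be summarized using descriptive statistics". The section states no period over which subjects are counted, no exposure adjustment and no separate table for the combination phase.

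The length of observation is set elsewhere:

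- Section 3.1.16: "On Study Follow-up will be conducted for 100 days after the last study drug administration". Section 7.1.5 says that during this follow-up all AEs "will continue to be collected for 100 days after the last dose of study drug administration".
- Section 3.1.12: "Treatment extension with nivolumab monotherapy beyond 18 weeks is permitted and will be managed at the Investigator's discretion". No maximum is given. Section 3.1.15 gives a nominal treatment duration of one year and lets subjects who benefit continue.
- Section 3.2, footnote g: "After Week 18, LDH testing and TSH (with reflexive free T3/T4) testing during ongoing nivolumab treatment will be done as clinically indicated". Other testing is unchanged. Under footnote d, visits stay 2-weekly on 240 mg and become 4-weekly only on the 480 mg option.

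The Amendment 5 entry in Section 8.1 explains footnote g: "the change was added only for ongoing treatment period after Week 18 to allow for the core study to have consistent collection of data".

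The only fixed safety window is in Section 3.1.9. It covers the first two cycles, up to the Cycle 3 pre-dose assessments, and serves only the decision to open Cohort B.

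**The concern.** A count of subjects with an event can only grow as observation lengthens. Here a subject who stopped after one dose and a subject treated for a year or more enter the same numerator and denominator, although one is observed several times longer than the other. A reader of the table cannot tell whether a count reflects the combination phase with radiotherapy or months of later nivolumab.

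The planned difference between the cohorts is the radiotherapy schedule, and Section 2.2 names dose and fractionation as a question worth studying. Readers will therefore look at the two cohorts' counts side by side, even without a formal test. Cohort B opens only after Cohort A has been reviewed, so the mix of extension lengths need not be the same in both.

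The Amendment 5 rationale treats the period to Week 18 as a core study with consistent data collection. Section 4.1.2 makes no use of that period.

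**Working it through.** **1. The plan's own figures.** Section 3.1.6 gives the Cohort A limit as 7 of 9, or 78%; 7/9 = 77.8%, which agrees. Study day = (week − 1) × 7 + 1 reproduces the flowchart days: Week 4 = Day 22, Week 7 = Day 43, Week 10 = Day 64, Week 18 = Day 120.

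**2. End of AE observation.** Input: 100 days after the last dose (Sections 3.1.16 and 7.1.5), with complete follow-up. Taking one year as Day 365:

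| Last dose | Calculation | Observation ends |
|---|---|---|
| Day 1 only | 1 + 100 | Day 101 |
| Fourth combination dose | 64 + 100 | Day 164 |
| Week 18 | 120 + 100 | Day 220 |
| One year | 365 + 100 | Day 465 |
| Beyond one year | no stated limit | open |

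Ratios: 465/101 = 4.6 and 465/220 = 2.1. The last visit window (100–107 days) can add up to 7 days. Death, withdrawal of consent or loss to follow-up can end observation before Day 101.

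**3. Effect on one crude count (illustration).** The documents give no event-time distribution. Assume an AE with 20% risk by Day 220.

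- Constant hazard: F(d) = 1 − 0.8^(d/220). F(101) = 9.7%, F(220) = 20%, F(465) = 37.6%.
- Hazard falling to 25% of its early value after Day 120: time is weighted as 120 + 0.25 × (d − 120) beyond Day 120, so Day 220 counts as 145 and Day 465 as 206.25. F(101) = 14.4%, F(220) = 20%, F(465) = 1 − 0.8^(206.25/145) = 27.2%.

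**4. Effect on two cohorts with equal hazards (illustration).** Assume 2/9 of one cohort and 6/9 of the other continue to one year and the rest stop at Week 18. With 20% risk by Day 220 and constant hazard:

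- 2/9 × 37.6% + 7/9 × 20% = 23.9%
- 6/9 × 37.6% + 3/9 × 20% = 31.7%
- gap 7.8 points

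For risks of 10% to 30% by Day 220 and either hazard shape, the gap runs from 1.7 points (10%, falling hazard) to 10.2 points (30%, constant hazard). If extension is the same in both cohorts, the gap is 0. One subject in 9 is 11 points.

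**5. Subjects with any Grade 3/4 event.** Only subjects still event-free can add to this count. Assume 1–3% risk per month after Week 18. The extra 465 − 220 = 245 days are 245/30.44 = 8.05 months, so 1 − exp(−0.01 × 8.05) = 7.7% and 1 − exp(−0.03 × 8.05) = 21.5% among those event-free. If 53% (the rate cited in Section 3.1.6) had already had an event, the addition is 0.47 × 7.7% = 3.6 to 0.47 × 21.5% = 10.1 points, or 0.3 to 0.9 of 9 subjects. That is an extreme contrast: all of one cohort extends to a year and all of the other stops at Week 18.

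**6. Detection after Week 18.** LDH is one of 16 listed chemistry analytes. It and the three thyroid tests lose their fixed schedule; the other 15 analytes, amylase, lipase and blood counts keep theirs. From Week 20 to Week 52 there are 17 visits on the 2-weekly schedule and 9 on the 4-weekly one. Less testing lowers late counts and longer exposure raises them, so the net direction cannot be derived.

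**7. When AE collection ends.** Section 4.1.1 says the End of Study Visit, a name no flowchart column carries. Section 7.1.5 covers AEs "occurring between the date of signing the informed consent and the off-study date". Section 7.1.5 and Section 3.2 footnote a also say 100 days after the last dose. These are three descriptions of one limit.

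**The case against.** The strongest reply is that the plan makes no cohort comparison. Section 3.1.6 calls the study descriptive, enrolment is sequential and not randomized, and with 5 of 9 subjects affected the exact 95% interval is about 21% to 86%. No choice of window would make the cohorts formally comparable. That stands, and it limits what a common window can achieve. It does not answer the point, because descriptive counts are the study's main product and a count without a stated period is hard to interpret even within one cohort.

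A second reply is that Section 4.1.2 leaves the analysis window open rather than equating it with the collection period, and that onset dates would allow phase-specific tables. That is correct. It means the choice would be made after the data are seen.

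A third is that a headline table cut at Day 120 would move late toxicity out of view, while Section 7.1.4 warns of very late immune effects. This also stands, and it is why the full-period table should stay.

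A reader might infer several stronger points that the documents do not support:

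- *Safety testing and visits are cut back generally after Week 18.* Only LDH and thyroid tests are relaxed, and visits thin out only on the 480 mg option.
- *Amendment 5 made detection differ by cohort.* This is possible, but no accrual or extension dates by cohort are given.
- *The counts cannot be set against the 53% rate.* The observation window behind that rate is not stated, so this is unproven either way.
- *The decision to open Cohort B is compromised.* Section 3.1.9 gives that review its own two-cycle window.

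**Conclusion.** The point holds in a limited form. The primary safety summary has no common window and no time at risk, while observation under the plan ends anywhere from about Day 101 to no fixed limit. Crude counts therefore depend partly on nivolumab duration. By-cohort counts are distorted only if extension differs between cohorts. The documents do not say whether it does, so the actual size and direction are unknown. The 1.7 to 10.2 points are an illustration resting on an assumed 2/9 versus 6/9 split, assumed risks of 10% to 30% by Day 220 and two assumed hazard shapes; equal extension gives zero. The change is worth making because it concerns the primary endpoint and is cheap.

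**What to change.** In Section 4.1.2:

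1. Keep the table of all AEs over the full collection period.
2. Add by-cohort tables of AEs and of Grade 3/4 AEs with onset from first dose through Day 120 (Week 18), whether or not treatment continues. Use the fixed day rather than the visit date. Report the number of subjects observed to Day 120: a one-dose subject is followed to Day 101, and a second dose at the early edge of its visit window (Day 19) gives Day 119.
3. Tabulate later-onset events separately, with subject-time at risk.
4. Reconcile Sections 4.1.1, 7.1.5 and 3.2 (footnote a) on when AE collection ends.

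The cost is some wording and one extra set of tables. Section 7.1.5 already requires onset dates, so no new data or visits are needed, and no event drops out of the report.
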